#### **6.2.4 Change from baseline in Pediatric quality of life inventory (PEDsQL)**

For the ITT population, the number and change from baseline in Pediatric Quality of Life Inventory (PedsQL) scores, including the generic core scales, gastrointestinal (GI) module, and neuromuscular module (NMM)

- CFB PedsQL =Post Treatment Measurement-Baseline
- CFB gastrointestinal (GI)= Post Treatment Measurement-Baseline
- CFB gastrointestinal (NMM)= Post Treatment Measurement-Baseline

For the derivation of PedsQL data, please refer to [Section 9.1.3](#).

In addition, the change from baseline in PedsQL total scores will also be summarized descriptively for the age cohort specified on the survey (5-7 years, 8-12 years, 13-17 years, 18-25 years, 26+ years (for Neuromuscular and GI modules, 18+ years is the highest age group)) by responder (parent and child), visit, treatment group and overall, for the ITT population:

PedsQL data and scores for each module and dimension, as well as the overall score, will be displayed.

### **6.3 Exploratory Endpoints**

#### **6.3.1 Change from baseline in QMT**

Change from baseline in quantitative muscle testing (QMT) to assess the muscle strength. Separate summaries will be provided for early stage DMD (LVEF > 45%) and advance (late) stage DMD (LVEF 35% - 45%) and combined (Early Stage + Late Stage).

Additionally, the number and percentage of subjects will be summarized by treatment group and overall.

- QMT
  - QMT Value = Collected on the CRF. Measured as the “best effort” of the 3 collected measurements at each time point where “best effort” = Max (QMT\_1, QMT\_2, QMT\_3)
  - Arm QMT Value = Sum of left elbow extension, left elbow flexion, right elbow extension, and right elbow flexion
  - Leg QMT value = Sum of left knee extension, left knee flexion, right knee extension, and right knee flexion
  - Total QMT Score = Sum of Arm QMT Value and Leg QMT Value
  - Indexed QMT Score = Arm, Leg, or Total QMT Score divided by subject age up to 20 years (lbs/years). For subjects >20 years of age, scores will be divided by 20.

A subject data listing of all QMT will be provided.

### 6.3.2 Change from baseline in daily life activity

Accelerometry was presented as an alternative approach for measuring physical activity and as a potential outcome measurement for DMD during this study.

Accelerometry:

Subjects wore an Actigraph accelerometer (Actigraph) on their dominant wrist and ankle for 7 days. Actigraph accelerometers were used to measure acceleration in three orthogonal axes (x, y, and z) at 30 Hz (i.e., 30 records per second per axis). ActiLife software (Actigraph, version 6.11.5 or higher) was used to upload accelerometer recordings, which were then integrated into 15s epochs and converted into an omni-directional acceleration estimate (VM), calculated as the square root of the sum of the triaxial signals squared, or  $(x^2 + y^2 + z^2)$ . Choi's method was utilized to distinguish between accelerometer wear and non-wear phases.

The accelerometer recordings of a participant were considered valid if they covered  $\geq 2$  days.

Wrist accelerometer recordings were divided into X min epochs while awake and used to calculate the time spent in activity intensity categories such as sedentary, low intensity, and moderate to vigorous physical activity (MVPA).

The adherence and physical activity parameters calculated for the wrist and ankle accelerometers of subjects with DMD included VMs generated while wearing (VM total), VMs generated per minute while wearing (VM/min wear), and VMs generated per minute while wearing and awake (VM/min awake).

It is necessary to undertake standard methods for the cleaning and management of accelerometer dataset.

Change from baseline in total VM Counts/min; VM Counts awake/min and physical activity intensities to assess the lifestyle behavior pattern will be provided.

Additionally, the number and percentage of subjects will be summarized by treatment group and overall.

## **6.4 Open Label Extension Analyses**

The open-label extension (OL) provides an opportunity to assess long-term safety and efficacy of high-dose ifetroban. Analyses will be performed for subjects completing 12, 24, and 36 months of treatment.

### **6.4.1 Efficacy Analyses in Open-Label Extension**

The following analyses will be performed for OL participants:

- One-year OL data (Month 12 to Month 24): Change from Month 12 in CMR parameters, PFT, QMT, and accelerometry will be summarized for all OL subjects, and by DB treatment assignment subgroups (High to High, Low to High, Placebo to High)
- Two-year total study data (Baseline to Month 24): Change from baseline in CMR parameters, PFT, QMT, and accelerometry will be summarized for continuous high-dose subjects compared to NHS matched subjects.
- Three-year total study data (for subjects completing 36 months): Change from baseline and from Month 36 in CMR parameters and PFT will be summarized

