8.1.3 Optional Open-Label Extension

Patients who complete 12 months of treatment are eligible to participate in a repeatable open-label extension period of 12 months. Should a subject elect to participate in the open-label extension, the transition from IMP to the open-label extension should be continuous. Patients who elect to participate in the open-label extension will complete the following additional procedures.

Month 15, 18 & 21 Phone Calls

- Inquire about AEs/Serious Adverse Events (SAEs) and IMP tolerability
- Record all medication use with start date and dose; check for prohibited medications
- Confirm compliance (subject diary & pill counting) & dietary requirement

- Remind subject to complete and return at-home PedsQL, GI module & NMM (**Month 18 only**)

Should the subject report a new or worsening symptom, additional safety phone calls and/or safety visits may be scheduled at the investigator's discretion and safety labs performed. Any new or worsening abnormal lab should be followed and repeated until back to baseline or resolved.

Month 18 At-home Quality-of-Life surveys

- Complete and return Month 18 at-home PedsQL, GI module & NMM

Month 24 Treatment Visit

After 12 additional months of treatment, subjects will return to the site for Month 24 Treatment Visit.

- Record all medication use with start date and dose; check for prohibited medications.
- Inquire about AEs/Serious Adverse Events (SAEs) and IMP tolerability.
- Confirm compliance (subject diary & pill counting) & dietary requirement.
- Perform ECG, a physical exam with vital signs (blood pressure, heart rate, respiration rate, body temperature, weight).
- Obtain blood samples for clinical laboratory tests:
 - Complete Blood Count with differential: must include hemoglobin, hematocrit, platelet count, total white blood cell count with five-part differential count, and total red blood cell count.
 - Comprehensive Metabolic Panel: must include serum creatinine, blood urea nitrogen, glucose, total protein, albumin, total bilirubin, alanine aminotransferase, aspartate aminotransferase, alkaline phosphatase, electrolytes (sodium, potassium, chloride), calcium, bicarbonate, and creatine phosphokinase.
 - Coagulation Factors: prothrombin time reported as the international normalized ratio (INR) value (PT-INR), partial thromboplastin time (PTT or aPTT).
- Collect urine and blood samples for eicosanoid metabolites and other biomarkers.
- Month 24 CMR (\pm 7 day window)

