11.1 Sample Size Determination

The sample size is based on the comparison of each dose level of ifetroban (Low Dose or High Dose) to placebo with respect to change from baseline in LVEF using CMR for each disease stage, early (LVEF > 45%) or advanced (current/historical LVEF 35-45%). Assuming observations from each treatment group have normal distributions with an effect size of 1.6 for the comparison of a dose of ifetroban to placebo, 8 subjects for each treatment group within disease stage will provide

power exceeding 85% for a t-test at two-sided level 0.05. Under these assumptions, 8 subjects for each treatment group within disease stage will provide power exceeding 80% for the Wilcoxon rank sum test at two-sided level 0.05. A total of 48 DMD subjects will be enrolled: 24 subjects with early stage DMD (LVEF > 45%) and 24 with advance stage DMD (current/historical LVEF 35-45%). Assuming a dropout rate of 25%, 60 subjects will be recruited to meet the target sample size of 48 subjects.

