11.8.6 Long-Term Safety and Efficacy Analyses

Subjects that complete the 12-month double-blind portion of the study will be eligible for an optional open label extension consisting of repeatable 12-month periods of treatment with high-dose ifetroban.

Safety will be monitored by continual adverse event reporting and changes in laboratory values as previously described.

For main efficacy endpoints (CMR parameters LVEF and myocardial strain), comparisons with respect to the change from Month 12 in LVEF and the change from Month 12 in myocardial strain at Months 24 and 36 will be performed for the ITT open label population using the Wilcoxon rank sum test. To assess treatment response the double-blind and open label studies, comparisons with respect to the change from baseline in LVEF and the change from baseline in myocardial strain at Months 24 and 36 will be performed for the ITT open label population using the Wilcoxon rank sum test. Subjects missing LVEF at either Month 12 or Month 24 will be excluded from this supportive analysis.

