#### 3.1 Study Design

This is a double-blind (DB), placebo-controlled, multicenter, dose-ranging study with an open-label extension (OL) to determine the safety, pharmacokinetics, and efficacy of two dose ranges of oral ifetroban in subjects with DMD.

[figure not shown]
Subjects who meet eligibility criteria will be randomly assigned to one of three treatment groups 1:1:1 ratio, low-dose ifetroban, high-dose ifetroban or placebo, and dosed based on weight. Each treatment group will be evaluated by eight subjects with early stage (LVEF >45%) and eight subjects with advance stage (LVEF 35% - 45%) DMD for at least six months and a maximum of 12 months. Subjects who complete 12 months of treatment will be eligible to participate in an OL extension ([Figure 1](#)).

All subjects who receive IMP will be assessed for safety. All subjects with at least one efficacy assessment post-baseline will be evaluated for efficacy. Blood and urine will be collected for standard and novel cardiac biomarkers.

The clinical study will be conducted with two periods:

- Screening period of up to 12 weeks.
- Randomized ifetroban/placebo treatment period of 12 months.
- Subjects who complete 12 months of treatment will be eligible to participate in an OL extension.

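### The Month 24 comparison of continuous high-dose subjects with natural history, and the Protocol's Month 36 comparison, select their two sides differently after baseline, in a direction the documents do not settle

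*SAP*

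**What the plan says.** SAP 6.4 sets the scope of the extension analyses: "Analyses will be performed for subjects completing 12, 24, and 36 months of treatment". SAP 6.4.1 then states "The following analyses will be performed for OL participants", and its two-year item, Baseline to Month 24, "will be summarized for continuous high-dose subjects compared to NHS matched subjects". SAP 14.3.7 repeats the pairing (High to High against NH) and tests change from baseline with the Wilcoxon rank sum test.

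Entry to the extension has two conditions. Protocol 8.1.3 gives the first: "Patients who complete 12 months of treatment are eligible to participate in a repeatable open-label extension period of 12 months". The second is that the subject elects to take part, since the extension is optional. SAP 4.2 adds a third condition for the analysis: subjects without Month 24 or Month 36 data are left out and nothing is imputed.

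For the NHS side, SAP 14.3.3 requires two years of LVEF data, no history of heart failure, and live subjects with cardiac data at baseline and Month 12 and at Month 12 and Month 24. (SAP 14.3.1 words the data condition the opposite way round; I take 14.3.2 and 14.3.3 as intended.)

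Protocol 11.5 plans to compare NHS subjects with open-label high-dose subjects at Months 12, 24 and 36. The Protocol synopsis calls the NHS the primary comparator for the extension.

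**The concern.** The two-year change is counted from study baseline, but membership of the ifetroban group is settled a year or more later, on treatment. A high-dose subject who stops in year 1, or finishes and declines the extension, has a baseline CMR and should have a Month 12 or End of Treatment CMR, yet has no place in the result. If leaving is related to how the heart is doing, the remaining group is not the group that was randomised.

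The NHS controls are also a selected group, but by different rules. After Month 12 there is no concurrent placebo, so nothing inside the trial would show how far the two selections differ. A difference at Month 24 could then partly reflect who was left to be measured.

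The Month 12 to Month 24 analysis starts its clock after entry to the extension, so it is not affected in the same way.

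**Working it through.** **1. The plan's own figures.** The documents give no sample size, power or retention figure for the two-year comparison. The nearest input is dropout.

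- Protocol 11.1: "Assuming a dropout rate of 25%, 60 subjects will be recruited to meet the target sample size of 48 subjects". With 1:1:1 allocation, 60/3 = 20 start on high dose and 20 × 0.75 = 15 finish, so 5 of 20 are lost. (48 × 1.25 = 60 reproduces the stated figure; 48/0.75 would be 64.)
- SAP 3.4: 10% dropout, 54 recruited. 54/3 = 18 start and 18 × 0.90 = 16.2 finish, so about 2 of 18 are lost.

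Declining the extension and missing a Month 24 CMR would add to either loss. The documents give no rate for these.

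**2. The two filters side by side.**

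| Step after baseline | Continuous high-dose | NHS |
|---|---|---|
| Tolerate drug and complete 12 months | required | no counterpart |
| Elect to continue | required | no counterpart |
| Later cardiac data present | required | required |
| Alive at the later visit | implied by having data | stated |
| No history of heart failure | at trial entry only: no heart failure admission in the prior 12 months | stated, undated |

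**3. Shift if only the ifetroban side is selected (assumed).** Suppose there is no true effect, a share r is retained by best Month 12 change, and Month 12 and Month 24 changes correlate at ρ. With c = Φ⁻¹(1 − r), the mean Month 24 change of those retained shifts by ρ × φ(c)/r SD.

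- r = 0.75: φ(c)/r = 0.318/0.75 = 0.424. For ρ = 0.4, 0.6, 0.8 the shift is 0.17, 0.25, 0.34 SD.
- r = 0.90: φ(c)/r = 0.1755/0.90 = 0.195. The shift is 0.08, 0.12, 0.16 SD.

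Simulation at the actual group sizes, with 2:1 unselected controls and a two-sided 5% Wilcoxon test:

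| Kept | Shift, ρ = 0.4 / 0.6 / 0.8 | Two-sided error |
|---|---|---|
| 15 of 20 | 0.16 / 0.24 / 0.32 SD | 8% / 12% / 18% |
| 16 of 18 | 0.08 / 0.12 / 0.16 SD | 6% / 7% / 8% |

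A smaller group (12 kept of 16) gives 6.6% error at ρ = 0.4. Rounded outward over runs, the ranges are 0.16–0.33 SD and 6–18% at 25% loss, and 0.08–0.16 SD and 5–8% at 10% loss.

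**4. Shift if the NHS side is selected too (assumed).**

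- Same share and same ρ on both sides: the terms cancel and the net shift is 0.
- NHS keeps 60% (φ(c)/r = 0.644) and ifetroban 75%, same ρ: ρ × (0.424 − 0.644) = −0.22ρ, which is −0.09, −0.13, −0.18 SD for ρ = 0.4, 0.6, 0.8.
- NHS 60% with ρ = 0.5, ifetroban 75% with ρ = 0.25: 0.106 − 0.322 = −0.216 SD, against ifetroban.

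The correlations and the NHS retention are assumptions; the documents supply none of them.

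**The case against.** A reader might infer that the plan removes subjects who do badly on ifetroban and so favours the drug at both two and three years. The documents do not support that much.

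- **Direction.** NHS subjects must also be alive with complete data and have no history of heart failure, so poor outcomes leave that side as well. Figures computed against unselected controls describe an upper end, not the planned comparison. This stands.
- **Decliners.** Protocol 7.3.1 and 7.4 let a subject whose LVEF falls by more than 5% change cardiac medication and remain on study drug. The toxicity exits in Protocol 7.2 are not shown to follow LVEF. Losing the worst subjects is therefore an assumption. Permission to stay does not, however, prevent withdrawal or opting out.
- **Three years.** The SAP item "Three-year total study data (for subjects completing 36 months") is not limited to high dose and names no NHS arm. Protocol 11.8.6, where comparisons "at Months 24 and 36 will be performed for the ITT open label population using the Wilcoxon rank sum test", names none either. The Month 36 point rests on Protocol 11.5 alone, which does not say whether change is counted from baseline or Month 12.
- **Sample size.** The 16 per arm is the target after dropout. Taking 25% off it would count the loss twice.
- **Already handled.** SAP 6.4.2 plans mixed models over the whole study by double-blind assignment, and SAP 4.5.3 labels NHS results supplementary. The model has no defined population and no NHS arm, so it does not answer the point. The label limits the weight of the result but does not change who is in it.

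**Conclusion.** The point holds in this form: at Month 24, and at Month 36 where the NHS comparison is made, the ifetroban and NHS groups pass different filters after baseline. No analysis of all subjects randomised to high dose against NHS is planned. About 5 of 20 (Protocol) or 2 of 18 (SAP) high-dose subjects fall outside the result before any opt-out.

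The sign of the net bias cannot be fixed from the documents. A tilt towards ifetroban is plausible, because completing and electing have no NHS counterpart. Its upper end is 0.16–0.33 SD with about 6–18% two-sided error at 25% loss, and 0.08–0.16 SD with about 5–8% at 10% loss. Those figures assume loss strictly by Month 12 change and unselected controls. The net shift is about zero under equal selection and negative if the NHS filter is the stronger. The primary safety endpoint and the randomised Month 12 comparisons are not touched by this point.

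**What to change.** In SAP 6.4.1 and 14.3.7:

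- Add a sensitivity analysis of change from baseline to Month 24, and to Month 36 where NHS is the comparator, in all subjects randomised to high dose with a baseline CMR.
- Use a repeated-measures model on the annual CMR visits, with the End of Treatment CMR for early stoppers (Protocol 8.1 and 9.1 already ask for it). Month 6 is best left out: that CMR is optional and NHS visits are yearly.
- Match NHS subjects at study baseline. The open-label matching in SAP 14.3.3 and 14.3.4 uses Month 12 as baseline. Do not require NHS subjects to be alive with complete Month 12 and Month 24 data, and drop the two-years-of-LVEF condition for this analysis. Restoring only the ifetroban side would create the opposite imbalance.
- Label the High-to-High Wilcoxon result a completers' analysis.
- Tabulate baseline LVEF and last observed LVEF change for high-dose subjects who did and did not enter the extension.

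In simulations where dropout depended on Month 12 change, a likelihood-based analysis with the same entry conditions on both sides brought the shift to about 0 SD. The cost is SAP text, a second matching run and one model on data the studies already collect. The model relies on data being missing at random after the last observed CMR, which these data cannot verify.

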Endpoints collected during both the double-blind and open label portions of the study will be compared with a U.S. Food and Drug Administration (FDA)-funded DMD natural history study (NHS) with similar endpoint design and yearly study visits. NHS data from patients matched by age, baseline LVEF, and background DMD therapy to CPI-IFE-007 study subjects will be used to supplement the placebo arm of the double-blind portion of the study and will be used as the primary comparator for data collected during the open-label extension.		

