11.5 Historical Comparator

Data collected from an FDA-funded DMD NHS will be used as a historical comparator/supplemental placebo group ([Soslow 2023](#)). The NHS utilized as a comparator is an ongoing, multi-year, multicenter study evaluating the natural progression of DMD. Eligibility is broad based on DMD diagnosis, and endpoints collected mirror endpoints collected for CPI-IFE-007 except patient-reported outcomes (PedsQL). NHS visits are scheduled yearly, and demographic, baseline characteristics, medical history, and concomitant medication information is collected at each visit along with CMR, PFTs, QMT, and accelerometry. Patients from the NHS will be selected at a 2:1 ratio (NHS to placebo) using propensity score matching (PSM) based on baselined LVEF, age, and background DMD therapy with consideration for other relevant cardiac medications (ACEi, ARB, beta-blockers, ARNI, aldosterone receptor antagonists, diuretics, calcium channel blockers. Matched NHS patients will be added to the CPI-IFE-007 placebo group from the 12-month double-blind study to create a supplemental, representative placebo group of a larger size for Month 12 efficacy analyses. For the open label extension, a historical comparator group will be formed from NHS patients selected at a 2:1 ratio (NHS to open label high-dose ifetroban) using PSM as described above. The NHS comparator group for the open label extension will be compared with open-label high-dose ifetroban patients at Month 12, Month 24, and Month 36.

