11.8.3 Efficacy Analyses

Between-treatment comparisons with respect to the change from baseline in LVEF and the change from baseline in myocardial strain at Month 6 and Month 12 will be performed for the ITT and PP Populations using the Wilcoxon rank sum test. A supportive analysis with missing LVEF at Month 12 imputed by LVEF at Month 6; subjects missing LVEF at both Month 6 and Month 12 will be excluded from this supportive analysis. In line with the current paradigm for the assessment of therapeutic efficacy in rare diseases and specifically DMD using established natural history data ([Liu 2022](#), [US FDA 2019](#), [US FDA 2018](#)), a comparison of the NHS-supplemented placebo group (2:1 NHS to placebo) will also be performed at Month 12 versus the high-dose ifetroban ITT and PP populations for CMR parameters.

Summary statistics for other endpoints will be presented for both the ITT and PP Populations.

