#### **4.4.4 Multiple Comparisons/Multiplicity**

Multiplicity and multiple comparisons do not apply to these secondary and exploratory objectives. No adjustments will be made for multiple comparisons or multiplicity. Changes to Protocol Specified Analysis

There are no changes to the protocol specified analyses.

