#### **14.3.7 Analysis with Natural History Data**

Multiple analyses will be completed using matched NH subjects as a historical comparator. See [Figure 2](#) below for a detailed analysis diagram.

In the DB study (Baseline to Month 12), the tables will be presented by the following treatment groups:

- ifetroban High
- Placebo with supplemented NH

In the OL study, the tables will be presented by:

[figure not shown]
One year data (Month 12 to Month 24):

- All OL
- High to High ifetroban
- Low to High ifetroban
- Ifetroban (High and Low combined)
- Placebo to High ifetroban
- NH

All study two-year data (Baseline to Month 24):

- High to High ifetroban
- NH

**Figure 2** All Study Analyses Diagram

For both the OL and the DB, demographic and baseline characteristics will be summarized for by treatment group including baseline LVEF, concomitant medication usage and propensity score by treatment group for the DB period and the OL period. Summary tables will be provided for the observed value and the change from baseline for each endpoint. In addition, 95% confidence intervals will be presented for each treatment group for the demographic variables and baseline characteristics. For categorical variables, proportion confidence intervals will be created using the binomial approximation.

A listing of natural history subjects' demographic and baseline characteristics will also be included.

For the DB period, the endpoints CFB in LVEF and myocardial strain at 12 Months. For the OL period, the endpoints to be evaluated at the 24 months after treatment are CFB LVEF, CFB myocardial strain, PET, QMT, and accelerometry. All endpoints will be evaluated using the change from baseline will be compared between the ifetroban vs. Placebo or natural history groups using a Wilcoxon rank sum test

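### The protocol compares extension subjects with natural history at Month 36; the SAP specifies no such comparison, uses Month 36 as its own reference visit, and declares no change

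*SAP*

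**What the plan says.** **Protocol.** The synopsis states that matched NHS data "will be used as the primary comparator for data collected during the open-label extension". Section 11.5 gives the visits: the NHS group "will be compared with open-label high-dose ifetroban patients at Month 12, Month 24, and Month 36". Section 11.8.6 adds that comparisons of change in LVEF and strain "at Months 24 and 36 will be performed for the ITT open label population using the Wilcoxon rank sum test", once with Month 12 as the reference and once with baseline. Section 6.5 lists efficacy over 24 to 36 months among the secondary endpoints.

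**SAP.** Section 6.4.1 covers the third year in one line: "Three-year total study data (for subjects completing 36 months): Change from baseline and from Month 36 in CMR parameters and PFT will be summarized". The bullet directly above it, for two-year data, does name matched NHS subjects. The latest NHS comparison period in section 14.3.7 is headed "All study two-year data (Baseline to Month 24"). Section 14.3.3 names baseline, Month 12 and Month 24 as the visits at which NHS candidates for open-label matching need cardiac data. Section 4.4.4 nevertheless says "There are no changes to the protocol specified analyses", and section 8, which is reserved for departures from the protocol, is marked not applicable.

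**A smaller mismatch in the double-blind period.** Protocol 11.8.3 says that comparisons of LVEF and strain "at Month 6 and Month 12 will be performed for the ITT and PP Populations using the Wilcoxon rank sum test". SAP 6.2.1 names the ITT population only and mentions no Month 6 test.

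**The concern.** Everyone in the extension takes high-dose ifetroban, so there is no concurrent untreated group after Month 12. DMD cardiomyopathy is progressive. A three-year fall or plateau in LVEF among treated subjects cannot be read as benefit, or as lack of it, without knowing what comparable untreated subjects do over the same interval. The protocol relies on the NHS for that.

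If the Month 36 comparison is left out of the SAP and built later, several choices would be made after treated results are visible: the reference visit, the population, the index visit for matching and the follow-up required of NHS subjects. The statement that nothing has changed also means a reader of the SAP would not learn that a protocol analysis had gone.

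**Working it through.** No power or effect figure bears on this point, so the check is a side-by-side reading plus one line of arithmetic.

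**1. Month 36 in the two documents**

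| Element | Protocol | SAP |
|---|---|---|
| NHS comparison visits, extension | Months 12, 24 and 36 (11.5) | Month 12 to 24 and baseline to Month 24 (14.3.7) |
| Test at Month 36 | Wilcoxon rank sum, LVEF and strain (11.8.6) | None named; summary only (6.4.1) |
| Reference visits for Month 36 change | Baseline and Month 12 (11.8.6) | Baseline and Month 36 (6.4.1) |
| NHS visits required for matching | Not stated | Baseline, Month 12 and Month 24 (14.3.3) |
| 24 to 36 month secondary endpoints | Listed (6.5) | Absent (3.3.2) |
| Assessment schedule | To Month 36 (Table 8-1) | To Month 24 (Appendix 1) |
| Departures declared | – | None (4.4.4 and 8) |

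The SAP says it follows Amendment 04a. With its endpoint list and schedule also stopping short of Month 36, an incomplete update is more likely than a deliberate decision to make Month 36 descriptive.

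**2. The reference visit**

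SAP 4.4.1 defines change as the later value minus the reference value. With Month 36 as both, change = value at Month 36 − value at Month 36 = 0 for every subject. Of the two changes promised in the three-year bullet, one carries no information.

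**3. Follow-up needed from NHS subjects**

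- Change from Month 12 to Month 36: 36 − 12 = 24 months after the open-label index visit.
- Change from baseline to Month 36: 36 − 0 = 36 months after the pre-treatment index visit.
- Visits named in SAP 14.3.3: 24 − 12 = 12 months after the open-label index visit, and 24 − 0 = 24 months after baseline.

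Each Month 36 comparison needs one yearly visit more than the named visits guarantee. Section 14.3.3 also asks for two years of LVEF data without saying from which visit. Even if that meant 24 months after the open-label index, it would cover LVEF from Month 12 to 36. It would not cover baseline to Month 36, and it says nothing about strain.

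**4. Double-blind period**

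Protocol 11.8.3 names Months 6 and 12, in ITT and PP. SAP 6.2.1 speaks of 12 months of dosing, names no Month 6 comparison, and gives ITT only. SAP section 6, its parent, assigns secondary efficacy analyses to both ITT and PP. The SAP is therefore silent on the Month 6 test and inconsistent with itself on the population.

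**The case against.** The best defence is that the SAP covers Month 36 elsewhere. Section 4.5.3 specifies a Wilcoxon comparison of all open-label ifetroban subjects with the NHS for the open-label period, and section 3.8 runs that period to the last study visit. Section 4.2 counts Month 36 among its key timepoints. Section 6.4.2 plans mixed-model slopes over the whole study by double-blind assignment. Section 14.3.7 refers to Figure 2 for the detailed layout.

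Some of this stands. A reader might infer that the SAP offers nothing but descriptive statistics for the third year, or that no comparator exists. That goes too far: the slope models are inferential and have internal comparison groups, and the NHS is described as ongoing and multi-year, so suitable data may exist. But 4.5.3 names no visit, 4.2 gives only an exclusion rule, and 6.4.2 names no NHS arm. The sections that would make an NHS comparison runnable stop at Month 24. Figure 2 was not available to check.

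Two other stronger readings also fail:

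- **That the SAP removed the PP analysis.** Section 6 retains PP for secondary efficacy; 6.2.1 merely fails to repeat it.
- **That a definite number of protocol tests was lost.** Protocol 11.8.6 names no comparison group for its rank sum tests, and 11.8.3 speaks only of comparisons between treatments, so any count depends on how those sentences are read.

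**Conclusion.** The mismatch is real and should be corrected before Month 36 results are examined. One of the three visits at which Protocol 11.5 compares the extension with the NHS has no specified counterpart in the SAP, one of the two three-year changes in SAP 6.4.1 is zero by construction, and the SAP denies any departure from the protocol. The consequence is lost prespecification of the external control at three years, on a secondary objective; no numerical bias is shown.

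This rests on two assumptions. First, the comparator for Protocol 11.8.6, which that section does not name, is taken from 11.5 and the synopsis. Second, Figure 2 is assumed not to add a Month 36 NHS analysis that the surrounding text omits. The Month 6 and population wording in SAP 6.2.1 is a lesser point of the same kind.

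**What to change.** 1. In SAP 6.4.1, replace the Month 36 reference visit with Month 12.
2. Extend SAP 14.3.3 and 14.3.7 to Month 36 with two comparisons of LVEF and strain by the planned rank sum test:
   - change from Month 12, all open-label subjects against NHS subjects matched at Month 12;
   - change from pre-treatment baseline, High-to-High subjects against NHS subjects matched at pre-treatment baseline.

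   Each should use NHS subjects who have the corresponding yearly visit. Limiting the second to High-to-High follows the SAP's own two-year analysis and keeps a year of placebo or low dose out of the treated change. Protocol 11.8.6 refers to the whole open-label ITT population, so record that limit in section 8.
3. If the sponsor does not want the Month 36 comparison, record its removal in SAP section 8, correct 4.4.4, and amend Protocol 11.5 and 11.8.6.
4. In SAP 6.2.1, state the Month 6 test or declare it dropped, and reconcile the population with section 6.

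**Cost.** Wording plus one more table set from yearly NHS visits. Few subjects are likely to have Month 36 data, and the number of NHS subjects with long enough follow-up is not stated, so intervals will be wide. That calls for modest claims, not for leaving the analysis undefined.
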